## 7.2 Severity Grading

The Investigator will grade all adverse events for severity. Adverse events listed in the Toxicity Grading Scale in [Appendix B](#) will be graded according to the criteria in the table. Adverse events not listed in the Toxicity Grading Scale will be graded as follows:

- Mild (Grade 1) – No interference with activity
- Moderate (Grade 2) – Some interference with activity
- Severe (Grade 3) – Significant; prevents daily activity
- Potentially Life-Threatening (Grade 4) – ER visit or hospitalization
- Fatal (Grade 5)

These severity grades also apply to the Study Stopping Rules in [Section 7.10](#).

### 7.3 Causality Assessment

The Investigator will assess all AEs, including solicited AEs, for causality (relationship to study vaccine), assigning one of these three categories: Not Related, Possibly Related, and Probably Related.

An AE will be considered “Not Related” to study vaccine if **any** of the following conditions are met:

- An unreasonable temporal relationship between administration of the study vaccine and the onset of the AE (e.g., the event occurred either before, or too long after administration of the study vaccine for it to be considered related);
- A causal relationship between the study vaccine and the AE is biologically implausible (e.g. injury as a passenger in an automobile accident);
- A clear alternative causality for the AE is present (e.g. typical adverse reaction to a concomitant medication).

An AE will be considered “Possibly Related” if there is a reasonable possibility that the AE may have been caused by the study vaccine.

An AE will be considered “Probably Related” if there is evidence that the AE was caused by the study vaccine.

### 7.4 Follow-up of Adverse Events

The Investigator must follow all AEs until resolution, until the condition stabilizes or is no longer clinically significant, or until the subject is lost to follow-up. The requirement for follow-up includes solicited adverse events that continue past Day 8.

The Investigator is responsible for ensuring the conduct of any supplemental investigations considered necessary to evaluate the AE. These may include additional laboratory tests or investigations, histopathological examinations, or consultation with other health care professionals.

In the event of a non-fatal SAE, subjects will be instructed to contact the Investigator (or designee) immediately. All subjects experiencing an SAE will be evaluated by the Investigator or designee as soon as is feasible following the report of the SAE by the subject. In the event of a fatal SAE, the Investigator must provide the Sponsor with any available post-mortem findings, including histopathology.

Additionally, the Sponsor may request that the Investigator perform or arrange for the conduct of supplemental investigations for one or more AEs.

### 7.5 Reporting of Adverse Events

#### 7.5.1 Reporting Periods

The reporting period for SAEs begins at the time of informed consent and continues for the duration of study participation ([Section 5.14](#)). The reporting period for solicited AEs begins after

study vaccine administration on Day 1 and continues through Day 8. The reporting period for solicited AEs for the Placebo crossover subjects begins after VAXCHORA administration on Day 181 and continues through Day 188. The reporting period for all other AEs begins after study vaccine administration on Day 1 and continues through Day 29. The reporting period for all other AEs for the Placebo crossover begins after VAXCHORA administration on Day 181 and continues through Day 209. AEs that correspond to solicited AE terms and occur after Day 8 or Day 188 (for Placebo crossover subjects) will be reported as unsolicited AEs.

### 7.5.2 Documentation

The Investigator or designee will document all AEs in the subject's source documents and enter all unsolicited AEs or solicited AEs continuing after Day 8 in the adverse event eCRF within 7 days of awareness.

All unsolicited AEs should include:

- Event term
- Start and stop date
- Severity
- Seriousness (Yes/No) and Seriousness criteria met if applicable
- Relationship to study vaccine
- Action taken in response to the AE

### 7.6 SAE Reporting

The Investigator or designee must report all SAEs to the Sponsor Medical Monitor within 24 hours of their awareness of the event by filling out the paper SAE Form and send to [REDACTED]. The Investigator or designee must also enter SAEs in the adverse event eCRF.

The SAE Form should be completed as thoroughly as possible and signed by the Investigator or designee before reporting to the Sponsor Medical Monitor. The SAE Form must include an assessment of causality and should include a preliminary diagnosis if possible.

In order to avoid delays in initial reporting, additional information regarding the SAE may be provided as a follow-up report. The Investigator may also modify the diagnosis, seriousness, and/or causality assessment based on this information.

The Sponsor Medical Monitor will notify the Investigator of SAEs that meet criteria for expedited reporting to regulatory authorities. The Investigator is responsible for notifying the applicable IRB of these events and adhering to any other applicable local reporting requirements.

The Sponsor will report adverse events to FDA in accordance with 21 CFR 312.32. Specifically, the Sponsor will report unexpected fatal or life-threatening suspected adverse reactions no later than 7 days after initial receipt of the information, and serious and unexpected suspected adverse

reactions (SUSARs) no later than 15 calendar days after determining that the information qualifies for expedited reporting.

## 7.7 Other Events Requiring Immediate Reporting

### 7.7.1 Pregnancy

The Investigator or designee must submit the Pregnancy Report Form to [REDACTED] within 24 hours of their awareness of the pregnancy. All pregnancies will be followed to outcome. Additional information regarding the pregnancy may be provided as a follow-up report.

An uncomplicated pregnancy is not considered an AE. Complications of pregnancy may qualify as AEs or SAEs and would therefore be documented and reported as specified above.

### 7.7.2 Dosing Errors

The Investigator or designee must report any error in the dosing of study vaccine to the Sponsor Medical Monitor in a blinded manner, and report any unblinding information to the unblinded CRA within 24 hours of their awareness of the error. Additional information regarding the dosing error may be provided as a follow-up report. A dosing error without signs or symptoms is not considered an AE, but is a protocol deviation and may be determined to be an IPD.

### 7.7.3 Early Discontinuation for Safety Reasons

The Investigator or designee must report any early discontinuation for safety reasons to the Sponsor Medical Monitor within 24 hours of discontinuation ([Section 7.6](#)). Additional information regarding ongoing adverse events may be provided as a follow-up report.

### 7.7.4 Emergency Unblinding for Safety Reasons

The Investigator or designee must report emergency unblinding to the Sponsor’s Medical Monitor in a blinded manner within 24 hours of unblinding. The Investigator or designee must fill out the Unblinding Request Form and send to [REDACTED] and can discuss any unblinding information with the unblinded CRA. Additional information regarding the unblinding, excluding the actual treatment assignment, may be provided as a follow-up report.

## 7.9 Safety Monitoring Committee (SMC)

A Safety Monitoring Committee (SMC) will be appointed to conduct periodic review of all available interim, blinded safety data from simultaneous enrollment from all age cohorts every 6 months while study activities are ongoing. The SMC will be composed of two independent physicians and one independent statistician. The SMC charter will outline the specific data to be reviewed and the communication plan.

## 7.10 Study Stopping Rules

Enrollment will be stopped for any of the following:

1. Any death or SAE experienced by a subject, regardless of causality;
2. One or more subjects with a Grade 3 (severe) or greater AE assessed as possibly or probably related to the study vaccine.

The investigator or designee must suspend enrollment and notify the Medical Monitor at [REDACTED] within 24 hours of becoming aware of an event that meets either of the above rules. No specific notification form is required. Enrollment may be resumed following review of available safety data by the Sponsor's Medical Monitor and Safety Monitoring Committee and after the Sponsor's Medical Monitor has notified the Investigator that enrollment may resume.

For further information regarding Safety procedures, please refer to the PXVX-VC-200-006 Safety Management Plan (SMP) and PXVX-VC-200-006 SMC Charter.

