### 1.1.3 Summary of Findings from Clinical Studies

#### Safety

The safety of VAXCHORA was evaluated in four randomized, placebo-controlled, multicenter clinical trials. A total of 3235 adults 18 through 64 years of age received one dose of VAXCHORA and 562 received placebo [physiologic saline (N=551) or lactose (N=11)]. Overall, the mean age was 32.5 years; 53.8% of trial participants were female; 67.1% were White, 27.3% were Black or African American, 1.8% were Asian, 1.7% were multiracial, 1.3% were other, 0.6% were American Indian or Alaskan Native and 0.3% were Native Hawaiian or Pacific Islander. There were 9.3% Hispanic or Latino participants.

Adults 18 through 45 years of age received VAXCHORA in a multi-center, double-blind, randomized (8:1), placebo-controlled trial conducted in the United States and Australia. The safety analysis set included 2789 VAXCHORA recipients. Solicited adverse reactions were recorded daily for 7 days following vaccination. The most common adverse reactions (incidence > 3%) were tiredness (31%), headache (29%), abdominal pain (19%), nausea/vomiting (18%), lack of appetite (17%) and diarrhea (4%).

In a pooled analysis of the four clinical studies, 0.6% (20/3235) of VAXCHORA recipients and 0.5% (3/562) of placebo recipients reported a serious adverse event within 6 months post-vaccination. None of these events were considered to be related to vaccination. Refer to the VAXCHORA package insert for a complete summary of findings from clinical studies (VAXCHORA 2016).

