### 5.4 Randomization Procedure

On Day 1 pre-vaccination, medical history and concomitant medications will be updated in the subject file and negative urine pregnancy test confirmed, if applicable, and blood collected for immune response assessments. The Investigator will confirm and document the eligibility of each subject immediately prior to randomization. Subjects will be considered enrolled once a randomization number has been assigned. Delegated site staff users will enroll each subject by assigning and entering a Subject ID # in the Electronic Data Collection (EDC) system. The EDC user will access the integrated randomization function within the EDC system to randomize the subject to one of the treatment arms. Subjects will be randomized at up to 30 clinical research sites. The assigned treatment will appear only on the randomization schedule that will be delivered to unblinded study personnel before they enroll subject(s) at their site. Blinded study personnel will print the randomization number for each subject from the EDC randomization form and take it to the unblinded personnel, who will match the randomization number to the randomization schedule and dispense the associated treatment.

The study will be conducted as a double-blind study through Day 181, where neither the sponsor, the statistical team, study volunteer subjects, nor clinical site personnel (except for the unblinded staff), will know subjects' treatment assignment. Once each subject has reached their Day 181 visit

they will be individually unblinded. Once all safety and immunogenicity data have been received from the Day 181 visit and the data cleaned, and signed by the PI, preventing further changes, the biostatistics group will carry out the primary analysis. Subjects, clinical site personnel, Investigators and the sponsor will remain blinded until each subject has completed their Day 181 visit. Each subject is unblinded individually at Day 181 and at that time their active/placebo status will be recorded in the EDC. Refer to the current version of PXVX-VC-200-006 Unblinding Plan.

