### **5.20 Early Discontinuation**

An enrolled (randomized) subject is considered to undergo Early Discontinuation if they stop study participation before the study completion visit day of each group.

An enrolled subject may voluntarily withdraw consent for further participation at any time before the day of study completion. The Investigator will request (but cannot require) such subjects to provide the reason(s) for withdrawal of consent and to undergo an Early Discontinuation visit.

In addition, the Investigator, at his or her discretion, may withdraw a subject from further participation in the study. Criteria for withdrawal by the Investigator include:

- Noncompliance with the protocol
- Lost to followup: lost to followup requires documentation of at least 3 unsuccessful attempts to contact subjects. Lost to followup will be determined after subject's projected last visit day.
- Adverse event
- Other reason(s) which, in the opinion of the Investigator, indicates that continued participation in the study is not in the best interest of the subject

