##### **c) Placebo Crossover Groups only (Cohort 1, 2, 3): optional**

VAXCHORA will be offered to the subjects who were administered Placebo on Day 1 after unblinding.

The following will take place during this visit *prior to* Vaccination:

Subjects will take nothing by mouth (food or water) for 60 minutes before and after vaccination.

- Urine Pregnancy Test for Cohort 1 and 2
- Vital Signs

The following will take place during the visit and *after* vaccination:

- In-clinic evaluation of acute side effects for at least 30 minutes post-vaccination
- Acceptability/Palatability evaluation
- Adverse event evaluation
- Memory Aid - distribution and training

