### 9.3 Treatment Groups

- Subjects in the active treatment group in each Cohort at Day 1 will receive VAXCHORA.

Cohort 1: 12 to <18 years (Active treatment group: n=150)

Cohort 2: 6 to <12 years (Active treatment group: n=150)

Cohort 3: 2 to < 6 years (Active treatment group: n=210)

- Subjects in the Placebo crossover group in each Cohort at Day 181 ( $\pm 7$ ) will be offered VAXCHORA.

Cohort 1: 12 to <18 years (Placebo crossover group: n=25)

Cohort 2: 6 to <12 years (Placebo crossover group: n=25)

Cohort 3: 2 to < 6 years (Placebo crossover group: n=35)

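### The Section 7.10 stopping rule suspends only enrollment, so in the protocol text shown a trigger places no automatic hold on the optional Day 181 crossover doses (at most 85)

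*Protocol*

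**What the plan says.** Protocol section 7.10 lists two triggers: any death or SAE whatever its cause, and a single subject with a Grade 3 or higher AE judged possibly or probably related. The consequence is worded as "Enrollment will be stopped for any of the following". The site must then suspend enrollment and tell the Medical Monitor within 24 hours. The way out is also about enrollment: "Enrollment may be resumed following review of available safety data" by the Medical Monitor and the SMC. The section does not mention vaccination, dosing or the crossover.

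Section 5.4 says what enrollment means: "Subjects will be considered enrolled once a randomization number has been assigned". Section 5.20 uses the word in the same way: "An enrolled (randomized) subject is considered to undergo Early Discontinuation".

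Section 6.1.6(c) sets out the Day 181 crossover: "VAXCHORA will be offered to the subjects who were administered Placebo on Day 1 after unblinding". Before the dose it asks for fasting, a pregnancy test in Cohorts 1 and 2, and vital signs. It does not refer to 7.10.

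Section 7.9 schedules SMC review "every 6 months while study activities are ongoing". Section 7.10 sends the reader to a Safety Management Plan and an SMC Charter for further safety procedures.

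**The concern.** The crossover is a second period in which children receive the live vaccine for the first time. The dose is optional and is given to healthy children after unblinding. A stopping rule would be expected to cover every planned administration of the study vaccine. This one, read as written, covers only the Day 1 administrations.

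A site could follow 7.10 exactly and still give a crossover dose while a safety review is open. A site with its own trigger has to contact the Medical Monitor and can ask what to do. The protocol text shown does not tell the other sites (up to 30 in all) that pending Day 181 doses should wait. What is at stake is the protection of participants; no efficacy or immunogenicity inference depends on it.

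**Working it through.** **1. Number of crossover doses.** Section 9.3 gives placebo crossover groups of 25, 25 and 35. The sum is 25 + 25 + 35 = 85. Active groups: 150 + 150 + 210 = 510. Total: 510 + 85 = 595, which reproduces the planned total in Table 3. The 6:1 ratio agrees: 595/7 = 85. Crossover vaccination is optional, so 85 is a ceiling, equal to 85/595 = 14.3% of the largest possible number of VAXCHORA doses.

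**2. Does the rule reach those doses?**
- 7.10: stop, suspend and resume all act on enrollment.
- 5.4 and 5.20: a subject is enrolled at randomization.
- 6.1.6(c): crossover recipients were randomized and given placebo at Day 1.

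Suspending enrollment therefore stops new randomizations and leaves crossover dosing unaddressed.

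**3. Is the hold carried to Day 181 elsewhere?** Other pre-dose safeguards are carried there explicitly: the pregnancy test in 5.9 and the prohibited medications in 5.16. The stopping rule is not. The schedule in Appendix A shows no eligibility check at the crossover visit.

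**4. Timing.** Day 181 ±7 is Day 174 to Day 188, which is 174 − 1 = 173 to 188 − 1 = 187 days after Day 1. A child given placebo in about the last six months of accrual is therefore due after enrollment has closed. From then on, stopping enrollment changes nothing. Events are still collected from crossover recipients (unsolicited AEs to Day 209, SAEs to Day 365; section 5.14), so triggers can still occur.

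**5. What the protocol says about trigger frequency.** Section 1.1.3 reports SAEs in 20 of 3235 adult vaccinees and adds: "None of these events were considered to be related to vaccination". With 0 related SAEs in 3235, the one-sided 95% upper bound is 1 − 0.05^(1/3235) = 0.093%. Over 595 doses that is at most 595 × 0.000926 = 0.55 expected related SAEs, if the adult bound applies to children. For related Grade 3 or higher AEs the protocol gives no rate, although the threshold is low: one child with a possibly related headache severe enough to prevent daily activity would qualify (Appendix B).

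**6. Doses that would fall within one review.** If R crossover doses are spread evenly over T days and a review lasts L days within that period, about R × L/T doses fall inside it. The protocol gives neither L nor T. With assumed reviews of 1 to 4 weeks, assumed dosing over 12 to 24 months, and all 85 children accepting, the range is 85 × 7/730 = 0.8 to 85 × 28/365 = 6.5 doses per review. This is an illustration under assumptions, not an estimate.

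**The case against.** The strongest reply is that the protocol is silent here, not wrong, and that the answer may lie elsewhere. The Safety Management Plan and SMC Charter are cited but not shown, and section 7.8 on the Medical Monitor, who takes part in the 7.10 review, is not in the text available. Other controls also remain: 24-hour SAE reporting with a causality assessment (7.6), withdrawal by the investigator (5.20), termination by the sponsor (5.22), and SMC review that does not end with accrual (7.9). A stop limited to new randomizations can also be defended. The vaccine is licensed for adults, the strain has a long record that includes children, and the triggers are very sensitive.

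Much of this stands and limits the point. It does not remove it. None of those controls is an automatic hold on dosing, and sites work from the protocol.

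Two stronger readings are tempting, and the documents support neither:
- **That crossover dosing must continue during a review, or that no hold exists anywhere.** The protocol does not order dosing to go on, and the documents not shown may hold it.
- **That a large number of doses would be given during reviews.** A trigger equally likely in any of 85 crossover recipients leaves on average (85 − 1)/2 = 42 doses to come. At assumed related Grade 3 or higher rates of 0.1%, 0.5% and 1%, the chance of at least one such event among 85 recipients is 1 − (1 − p)^85 = 8%, 35% and 57%. These are ceilings under assumptions. The first counts every later dose as if the review never ended. The second is the chance of a trigger, not of a dose given during a review.

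**Conclusion.** The point holds for the protocol text shown. A 7.10 trigger places no automatic hold on Day 181 crossover vaccination, and the rule has no effect on dosing once accrual has closed. The ceiling is 85 doses, reached only if every placebo child accepts. The number that would fall within an open review cannot be derived from the protocol, since review length, dosing spread and the related Grade 3 or higher rate are all missing. The adult experience on related SAEs is reassuring, to the extent that it carries over to children.

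The conclusion rests on reading enrollment as sections 5.4 and 5.20 use it, and on no hold being written in the Safety Management Plan, the SMC Charter or section 7.8. If one is written there, what is left is a matter of aligning the protocol with it. Either way this is a cheap improvement worth making. It does not affect the primary analysis.

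**What to change.** Amend section 7.10 along these lines:

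- A possibly or probably related Grade 3 or higher AE, or a death or SAE not yet assessed as unrelated, suspends enrollment and all study vaccine administration, including Day 181 crossover vaccination, until the Medical Monitor and SMC have completed their review.
- SAEs assessed as unrelated continue to stop enrollment only.
- The rule applies until the last crossover dose has been given.
- A crossover dose held for this reason may be given outside the ±7-day window.

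Add a line to 6.1.6(c) that VAXCHORA is not given while such a review is open, with a cross-reference to 7.10. Check the Safety Management Plan and SMC Charter for agreement.

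Leaving unrelated SAEs out of the dosing hold keeps it proportionate. At the adult frequency in 1.1.3, about 510 × 20/3235 = 3.2 SAEs would be expected among Day 1 vaccinees within six months, and none of the adult events was judged related.

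The cost is a few sentences in an amendment and the delay of some optional crossover visits. No antibody sample is scheduled after the crossover dose (Table 4 and sections 6.1.7 and 6.1.8), so a delay loses no immunogenicity data.

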
STUDY PROCEDURES
	
Safety:
 
Subjects will be monitored for acute reactions for 30 minutes after vaccination. Adverse events of abdominal pain, headache, lack of appetite, tiredness, diarrhea, nausea, vomiting and fever will be solicited daily through Day 8 (and from Day 181 through Day 188 for Placebo crossover subjects) using a memory aid (diary card). Unsolicited Adverse Events (AEs) will be collected through Day 29, and Day 181 through Day 209 (for Placebo crossover subjects). Serious Adverse Events (SAEs) will be collected for the duration of

	
study participation. In Cohorts 2 and 3, events occurring after Day 29 will be assessed initially by telephone contact.
 
Immunogenicity:
 
Immunogenicity will be assessed by measurement of Serum Vibriocidal Antibodies (SVA) in all subjects at Days 1, 11, and 29. Subjects in Cohort 1 will have further measurements of SVA at Days 91 and 181. In the sub-study, subjects will have SVA measurements at Days 365, 547, and 730.
 
Study procedures are shown in the Schedule of Events (Appendix A)

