### 5.13 Solicited Adverse Events

Solicited adverse events for this study are: abdominal pain, nausea, vomiting, diarrhea, headache, lack of appetite, tiredness, and fever. From Day 1 through Day 8 (for all subjects) and from Day 181 through Day 188 (for Placebo crossover subjects), these adverse events will be solicited from subjects daily in the evening. Before discharge from the clinic on Day 1, all subjects will be trained to complete a memory aid to observe, measure, and record solicited AEs from Day 1 through Day 8. Study staff will review the signs and symptoms recorded on the memory aid with the subject to confirm severity and relationship to study vaccine, and action taken for the AE. The memory aid will be collected as a source document. Solicited adverse events from Day 1 through Day 8 will be recorded on the solicited adverse event eCRF. Symptoms continuing beyond Day 8 will be recorded on the adverse event eCRF. Actions taken for solicited AEs after Day 8 should be noted in the eCRF. Memory aid re-distribution and retraining to collect solicited adverse events from Day 181 through Day 188 (7 days after vaccination) will be done at Day 181 (vaccination) for Placebo crossover subjects. It will be reviewed by the study staff at the Day 191 (10 days after vaccination) visit.

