#### **Study Vaccine Administration:**

Subjects will take nothing by mouth (food or water) for 60 minutes before and after consumption of study vaccine.

The following will take place during the visit and *after* consumption of study vaccine:

- In-clinic evaluation of acute side effects at least 30 minutes post-vaccination
- Acceptability/Palatability evaluation
- Adverse event evaluation
- Memory Aid - distribution and training

### 6.1.3 Day 11

The following will take place during the visit:

- Memory Aid-collect and review
- Adverse event evaluation including SAE
- Blood Collection for:
  - Serum Vibriocidal Antibody (SVA)
- Updated concomitant medications

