#### 7.1.2 Solicited Adverse Event

A solicited adverse event (solicited AE) is a protocol-specified AE about which the Investigator or designee proactively asks the subjects during a protocol-specified time period. Solicited adverse events for this study are: abdominal pain, nausea, vomiting, diarrhea, headache, lack of appetite, fever, tiredness.

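### Stopping Rule 2 can act days late for severe reactions managed at home, because the first scheduled staff review of solicited events is Day 11

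*Protocol*

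**What the plan says.** Protocol 7.10 has two stopping rules. Rule 1 covers any death or SAE. Rule 2 is met by "One or more subjects with a Grade 3 (severe) or greater AE assessed as possibly or probably related to the study vaccine". The site must suspend enrollment and notify the Medical Monitor "within 24 hours of becoming aware of an event that meets either of the above rules". Restarting needs review by the Medical Monitor and the Safety Monitoring Committee (SMC).

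The information that feeds Rule 2 for solicited events is described in several places:

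- Section 7.1.2 defines a solicited AE as "a protocol-specified AE about which the Investigator or designee proactively asks the subjects during a protocol-specified time period". Section 5.13 adds that solicitation takes place each evening.
- The synopsis (Study Procedures) names the means. The events "will be solicited daily through Day 8 (and from Day 181 through Day 188 for Placebo crossover subjects) using a memory aid (diary card".
- Section 5.13 states what happens to the card: "Study staff will review the signs and symptoms recorded on the memory aid with the subject to confirm severity and relationship to study vaccine".
- Section 6.1.2 provides for "In-clinic evaluation of acute side effects at least 30 minutes post-vaccination" on Day 1.
- The next scheduled contact is the Day 11 visit (6.1.3), which lists "Memory Aid-collect and review". Appendix A gives that visit a window of 0 days in all three cohorts.
- After a crossover dose the card is handled the same way: "It will be reviewed by the study staff at the Day 191 (10 days after vaccination) visit".

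Three further provisions bear on earlier contact. Section 6.2 reviews solicited AEs at an early discontinuation visit before Day 11. Section 6.3 allows unscheduled visits, including for safety follow-up of an adverse event. Section 7.4 has subjects told to contact the Investigator at once, but only for a non-fatal SAE.

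**The concern.** A threshold of one related Grade 3 event is a first-case rule. Its value depends on the site hearing of the first case quickly. The events most likely to reach it after a live oral vaccine are the solicited ones, and the protocol has the family write these down on a card that staff first see at Day 11.

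Take a child with six loose stools in 24 hours on Day 2 who is cared for at home. Appendix B grades this as 3. Without an ER visit, hospitalization or another seriousness criterion, Rule 1 and the SAE contact instruction do not apply. Unless the family calls on its own, staff first review the event nine days later.

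Meanwhile the three age cohorts, down to age 2, enroll concurrently, so no age staggering acts as a backstop. The SMC looks at blinded data every 6 months and does not fill a gap of days. What is at stake is that some children may be dosed after an event that would have paused enrollment had the site known of it.

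**Working it through.** The protocol states no detection lag, so there is no figure of its own to reproduce.

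**Step 1. Scheduled lag.** Inputs: solicited onset on Days 1 to 8 (7.5.1) and review on Day 11 with window 0 (6.1.3, Appendix A). Lag = 11 − onset day.

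| Onset day | 1 | 2 | 3 | 4 | 5 | 6 | 7 | 8 |
|---|---|---|---|---|---|---|---|---|
| Lag (days) | 10 | 9 | 8 | 7 | 6 | 5 | 4 | 3 |

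The mean is (10 + 9 + 8 + 7 + 6 + 5 + 4 + 3)/8 = 6.5 days if onset is spread evenly, which is an assumption. A crossover dose on Day 181 with review on Day 191 gives the same values (191 − 181 = 10; 191 − 188 = 3).

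**Step 2. Lag that a call could remove.** Assume a same-day call and same-day assessment, then the full 24 hours of 7.10 used before the pause. Compare this with a pause made immediately at the Day 11 review. Avoidable lag = scheduled lag − 1 = 2 to 9 days. Slower assessment after the call would reduce it.

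**Step 3. Children dosed in that time.** The protocol gives no accrual rate, so I show a range. Assume 595 children enroll evenly over 24, 12 or 6 months, with 30.4375 days per month, no spontaneous call and a study-wide pause. The 6:1 allocation sends 6/7 of them to VAXCHORA.

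| Assumed enrollment period | Children per day | VAXCHORA in 2 days | VAXCHORA in 9 days |
|---|---|---|---|
| 24 months | 595/730.5 = 0.815 | 1.4 | 6.3 |
| 12 months | 595/365.25 = 1.629 | 2.8 | 12.6 |
| 6 months | 595/182.625 = 3.258 | 5.6 | 25.1 |

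For example, 3.258 × 9 × 6/7 = 25.1.

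**Step 4. Site-level pause.** Section 7.10 places the duty to suspend on the investigator or designee, so the pause can be read as local. With 30 sites accruing equally, divide by 30. The 2-day figures become 0.05, 0.09 and 0.19, and the 9-day figures 0.21, 0.42 and 0.84. All are below one child.

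**Step 5. Does anything scheduled shorten the lag?** In Appendix A the memory aid appears only at Day 1, Day 11, early discontinuation and the crossover visits. No cohort has a call or visit between Day 1 and Day 11.

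**The case against.** The strongest case against is that the protocol contains no error here. Rule 2 runs from awareness, and a site that acts within 24 hours of awareness complies. That stands. A reader might infer that the stopping rule contradicts the visit schedule, or that the site cannot learn of an event before Day 11. The documents support neither. Families may call, and 6.3 allows an unscheduled visit for a child who stays in the study. What 6.3 lacks is anything that prompts the call.

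A second argument is that evening solicitation in 5.13, with the wording of 7.1.2, implies that staff ask daily. The synopsis and Appendix A point the other way: the diary card is the means, and no contact is scheduled to carry out daily asking.

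Third, 7.10 refers to a Safety Management Plan and SMC Charter, which are not shown, and neither is the memory aid. Any alert may already be there. This stands, and it limits the point to what the protocol itself requires.

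Fourth, the affected class is narrow. Deaths and SAEs are covered elsewhere. Grade 3 vomiting in Appendix B needs IV hydration, and every Grade 4 row except fever involves an ER visit or hospitalization, so those families are already in care. Adult experience is reassuring too: 3235 recipients in four trials, with no SAE judged related to vaccination (1.1.3). This is fair, and it keeps the severity low.

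Finally, acting on telephone reports will produce some pauses for events later downgraded or judged unrelated. This stands and is counted as a cost below.

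**Conclusion.** The point holds as a cheap improvement of low severity. For a non-serious solicited AE that starts after the Day 1 observation in a child who stays in the study, the first scheduled staff review comes 3 to 10 days after onset, and a first-case pause can be that late. About 2 to 9 of those days could be avoided under the assumptions of Step 2.

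The number of children affected is unknown. The figure of about 25 might be read as an expected exposure, but it is an upper bound. It needs 6-month enrollment, a study-wide pause, Day 1 onset and no spontaneous call all together, and it says nothing about how often a related Grade 3 event occurs. Under a site-level reading of the pause, every scenario falls below one child. The pause is also reversible. For crossover doses the point matters only while enrollment is still open.

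**What to change.** In 5.13, 6.1.2 and 6.1.6(c), and on the memory aid, tell the subject or caregiver to phone the site the same day if any entry meets an Appendix B description of Grade 3 or higher. Have the Investigator assess grade and causality promptly on that report, using an unscheduled visit under 6.3 if needed. State that the 24-hour duty in 7.10 starts once the Investigator has assessed the event as Grade 3 or higher and at least possibly related, with confirmation at Day 11 or Day 191.

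The cost is a line on the card and in the Day 1 and Day 181 training, and a few unscheduled calls or visits. Some enrollment pauses will also prove unnecessary once the event is downgraded or judged unrelated, and each of these needs Medical Monitor and SMC review to lift. Thresholds, scheduled visits and samples do not change.

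If the Safety Management Plan or memory aid already carries this alert, conduct need not change, and a sentence in 5.13 saying so is enough.
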